1.0 BACKGROUND AND RATIONALE

1.1 Study Synopsis

The primary objective of the proposed research is to evaluate *in vivo* the diagnostic relevance of ultrasound-derived metrics for stiffness, elasticity, viscosity, and anisotropy. These biomarkers will be measured using novel, noninvasive ultrasound technologies under development in [name] laboratory: 1) Acoustic Radiation Force Impulse (ARFI) ultrasound for interrogating tissue stiffness, 2) Viscoelastic Response (VisR) ultrasound for assessing tissue elasticity and viscosity, and 3) Dynamic Displacement Anisotropy Imaging (DDAI) for measuring tissue anisotropy.

We hypothesize that ultrasound-derived stiffness, elasticity, viscosity, and anisotropy will detect lesion malignancy and predict response to treatment. To test this hypothesis, we will pursue the following specific aims:

Aim #1: Quantify the ability of ultrasound-derived stiffness, elasticity, viscosity, and anisotropy to detect malignancy. ARFI, VisR, and DDAI imaging will be performed on suspicious breast lesions in 40 women with BIRADS-4a, 4b, 4c, or -5 ratings. The diagnostic accuracy of imaging metrics will be analyzed, with malignancy confirmed by histology as the outcome.

Aim #2: Quantify the ability of ultrasound-derived stiffness, elasticity, viscosity, and anisotropy to predict a positive response to treatment. ARFI, VisR, and DDAI imaging will be performed serially over the course of neoadjuvant chemotherapy (NAC) - on malignant breast lesions in 40 women. Changes in outcome metrics over time will be correlated to overall reduction in tumor size (diameter and area). The ability of ultrasound metrics to predict a positive response to treatment will be examined. A positive response to treatment will be determined according to the Response Evaluation Criteria in Solid Tumors (RECIST) guidelines.^{1,2}

1.2 Disease Background (if applicable)

The primary objective of breast cancer screening is to identify early stage cancer, or precancerous lesions, at a time before symptoms emerge and when treatment is likely to result in a cure. Screening is beneficial when it averts progression of disease to metastasis and/or death, but adverse effects to patients (and unnecessary medical expense) may result downstream from false positives and indiscrimination of masses that will not respond to treatment. The sensitivity of digital mammography, the current screening standard in the US, has been reported in the range of 0.40 to 0.85,¹ with a positive predictive value of 0.31.² Sensitivity is increased by augmenting mammography with MRI and B-Mode ultrasound, but false positive rates may also increase³. There exists a vital need for a screening technology that exhibits high sensitivity and specificity for cancer detection with early identification of unresponsive masses.⁴

This urgent need could be met by exploiting new imaging biomarkers. Specifically, the mechanical properties of breast tissue have been used for cancer detection, with both elasticity⁵⁻⁸ and viscosity⁹ demonstrated for discriminating malignant from benign lesions. Further, tissue anisotropy has been shown to correlate with core biopsy result and tumor grade, with large cancers significantly more anisotropic than small cancers.¹⁰ Importantly, while both MRI and ultrasound can be used to measure these biomarkers, ultrasound's cost effectiveness and ease of implementation render it an efficient platform to pursue.

1.3 Diagnostic and Prognostic Studies

As stated above, *we hypothesize that ultrasound-derived tissue stiffness, elasticity, viscosity, and anisotropy will detect lesion malignancy and predict response to treatment.* Tissue property measures will be made using Acoustic Radiation Force Impulse (ARFI), Viscoelastic Response (VisR), and Dynamic Displacement Anisotropy Imaging (DDAI), which are described below:

Acoustic Radiation Force Impulse (ARFI) Imaging for Assessing Tissue Stiffness:

In ARFI imaging, the ultrasound transducer delivers an impulsive ARF excitation to the tissue near the position of the imaging focus, and, using the same transducer, the induced tissue displacement is monitored over time. Then, parametric images of ARFI-induced peak displacement (PD) are rendered to convey information regarding the relative stiffness of tissue, i.e. stiffer tissues achieve PDs that are smaller than those of softer tissues in response to a consistent ARF magnitude.¹¹⁻¹⁴ ARFI PD has been used by our group to characterize atherosclerotic plaques and delineate necrotic cores and fibrous caps. Fibrous cap thickness measurement ≥ 0.5 mm has been demonstrated to be within 10% error of histologically derived measurements. This, and previous work by others,¹⁵⁻²¹ suggest that ARFI will be similarly relevant for delineating stiffness differences in the breast that will be relevant for detecting necrotic cores, which could aid in discriminating malignant lesions and masses that do not respond to treatment.

Viscoelastic Response (VisR) Ultrasound for Assessing Tissue Elasticity and Viscosity:

Unlike ARFI, which primarily assesses tissue stiffness, VisR uses successive ARF excitations to interrogate tissue viscoelasticity.²²⁻²⁴ ViSR has been used to study muscle degeneration in boys with Duchenne Muscle Dystrophy. The ViSR measurements provided information on the changes in viscosity and elasticity of these muscles and were concordant with inflections in matched physical and quantitative muscle testing (QMT) results. The VisR results are also consistent with expected cycles of dystrophic degeneration. These data support that VisR will similarly be relevant to assessing viscous and elastic properties in the breast, which have been shown to be relevant to discriminating malignant from benign breast lesions^{5,6,8,9,25-27} and may be useful for distinguishing responsive from unresponsive masses.

Dynamic Displacement Anisotropy Imaging (DDAI) for Measuring Tissue

Anisotropy: Anisotropic tissue exhibits mechanical properties that are directionally dependent, i.e. the viscous and/or elastic properties of the material vary between one direction and another, and the degree of difference is referred to as the “degree of anisotropy.”²⁸ Anisotropy is interrogated in DDAI imaging using ARF that is configured to have an asymmetrical shape.²⁹ For example, in a transversely isotropic (TI) material, ARFI-induced PDs and VisR τ values are larger when the long axis of the asymmetrical ARF is aligned along versus across the material’s axis of symmetry (AoS). The ratio of induced PDs or τ values along versus across the AoS reflects the degree of anisotropy in the material. We have developed DDAI imaging using finite element method (FEM) simulations. These data suggest that DDAI imaging will differentiate breast lesions with anisotropic properties and/or AoS orientations that differ from those of the background breast tissue. Previous work suggests that DDAI-derived anisotropy information will correlate with breast core biopsy result, tumor grade, and tumor size^{10,30} and may be useful for differentiating malignant from benign lesions and responsive from unresponsive masses.

We will correlate ultrasound-derived stiffness, elasticity, viscosity, and anisotropy with response to treatment (Aim #2). Please see data analysis plans below for more information.

1.4 **Rationale**

In this exploratory clinical study, we will attempt to demonstrate that ARFI, VisR, and DDAI ultrasound reliably detect malignant breast masses (Aim #1) and distinguish masses that respond to chemotherapy from those that do not (Aim #2). The ARFI, VisR, and DDAI imaging location will be on the surface of the breast, above the suspicious or malignant mass. This unblinded, open-label, exploratory study will be conducted in 40 women with diagnosed BIRADS breast assessment categories of -4a, 4b, 4c, or -5 masses in Aim #1 and in 40 women with malignant masses undergoing neoadjuvant chemotherapy (NAC) in Aim #2. In Aim #1, patients will be recruited from those who have undergone breast imaging and are indicated for biopsy according to the routine standard of care at UNC Hospitals. Both diagnostic imaging and biopsy will be performed according to institutional standards and will not be altered for research purposes. In addition to standard radiologic examinations, the patients will undergo ARFI, VisR, and DDAI ultrasound imaging after BIRADS diagnosis but prior to biopsy. In Aim #2, patients will be recruited from those already undergoing NAC for treatment of breast cancer according to the standard of care at UNC Hospitals. NAC will be performed based on institutional standards and will not be altered for research purposes, except that we will perform serial ultrasound imaging over the course of treatment. The standard for clinical management during and after NAC will not be altered.

We will enroll participants in two groups, as patients with suspicious (Aim #1) breast lesions, or as patients with confirmed breast cancer undergoing clinically

indicated NAC (Aim #2). There will be no randomization to study arms and no intervention beyond ARFI, VisR, and DDAI ultrasound imaging.

1.5 Compliance Statement

This study will be conducted in full accordance to all applicable University of North Carolina (UNC) Research Policies and Procedures and all applicable Federal and state laws and regulations including 45 CFR 46, and the Health Insurance Portability and Accountability Act (HIPAA) Privacy Rule. Any episode of noncompliance will be documented.

The investigators will perform the study in accordance with this protocol, will obtain consent and assent (unless a waiver is granted), and will report unexpected problems in accordance with The UNC IRB Policies and Procedures and all federal requirements. Collection, recording, and reporting of data will be accurate and will ensure the privacy, health, and welfare of research subjects during and after the study.

2.0 STUDY OBJECTIVES

The purpose of this study is to evaluate *in vivo* the diagnostic relevance of ultrasound-derived stiffness, elasticity, viscosity, and anisotropy metrics for breast lesion malignancy and response to treatment.

2.1 Aim #1: Quantify the ability of ultrasound-derived stiffness, elasticity, viscosity, and anisotropy to detect malignancy.

In vivo ARFI, VisR, and DDAI imaging will be performed in 40 women with a breast mass with a BIRADS breast assessment categories of -4a, 4b, 4c, or -5 rating after diagnostic workup. First, the transducer will be placed lightly above the suspicious mass, just to the point of skin contact, to avoid pre-compression during imaging.¹⁵ The suspicious mass will be positioned at 10 to 40 mm in axial depth, with standoff used if needed to achieve the desired axial position. Second, the position of the transducer will be rotated through 90° in steps of 30° to identify the transducer position yielding maximum ARFI peak displacement in the mass. The transducer will be stabilized in this position, with light skin contact, by the sonographer or by using a stereotactic clamp. Third, ARFI and VisR data will be acquired in immediate succession. Fourth, the transducer will be rotated 90°, re-stabilized by the sonographer or by using the stereotactic clamp, and ARFI and VisR data will be acquired in the new transducer position to enable DDAI analysis. Finally, the evaluated mass will undergo clinically indicated biopsy with histological evaluation to determine if it is benign or malignant.

The ultrasound data will be processed to calculate the following outcome metrics: peak displacement (PD), displacement at a given time (TD) for ARFI; τ , relative elasticity (RE), relative viscosity (RV), and tissue mass (TM) for VisR; ratio of ARFI PD and ratio of VisR RE values at 90° versus 0° transducer orientations for DDAI. These eight outcome metrics, alone and in combinations, will be statistically correlated with biopsy finding of malignant or benign.

2.1.1 Determine which of the 8 ultrasound metrics best detects malignancy.

We will statistically evaluate all eight ultrasound outcome metrics independently to determine which metric best detects malignant finding.

2.1.2 Determine the combined diagnostic accuracy of any 2 ultrasound metrics.

We will systematically combine all possible groupings of two ultrasound outcome metrics. We will then determine which grouping of metrics best detects malignant finding.

2.1.3 Determine the combined diagnostic accuracy of ultrasound metrics and mammography.

For ultrasound outcome metrics (singly or combined) with AUC exceeding 0.75 in 2.1.1 and 2.1.2, we will determine if combining the metrics with mammography-derived mass size, density, shape, and margins improves ROC performance relative to not combining with mammography.

2.1.4 Determine which cutpoints for ultrasound metrics detect malignancy with optimum sensitivity and specificity.

Best-balanced cutpoints from the highest performing ultrasound metrics in 2.1.1 will be derived, and PPV will be calculated.

2.2 Aim #2: Quantify the ability of ultrasound-derived stiffness, elasticity, viscosity, and anisotropy to predict a positive response to treatment.

In 40 women with newly diagnosed invasive breast cancer who are scheduled to begin clinically indicated NAC, ARFI, VisR, and DDAI imaging will be performed (as described in Aim #1) immediately before beginning treatment and then over the course of treatment. The eight ARFI, VisR, and DDAI outcome metrics described in Aim #1 will be statistically correlated with clinically determined change in tumor size following NAC treatment. ARFI, VisR, and DDAI outcome metrics will also be evaluated for ability to predict positive response to NAC, with positive response determined according to the RECIST guidelines.^{1,2}

2.2.1 Determine which baseline ultrasound metric best predicts positive response to NAC.

We will statistically determine, from among all eight ultrasound outcome metrics acquired at each imaging time point, which metric best predicts positive response to treatment, with positive response determined according to the RECIST guidelines.^{1,2}

2.2.2 Determine which baseline ultrasound metric correlates most strongly with absolute reduction in tumor size.

We will correlate absolute change in tumor size (diameter and area) from baseline to end of chemotherapy type with ultrasound metric values at baseline.

2.2.3 Determine the combined ability of any 2 baseline ultrasound metrics for prediction of positive response to NAC.

We will systematically combine all possible groupings of any two ultrasound outcome metric values at baseline. We will then statistically analyze the combined ability to predict reduction in tumor size.

2.2.4 Determine if serial changes in ultrasound metrics correlate with positive response to NAC.

We will evaluate the correlation of serial changes in ultrasound metrics with tumor size. Assessments of serial change will be made at 3 intervals per chemotherapy type: baseline, early chemotherapy type treatment, and end of chemotherapy type treatment.

2.2.5 Determine for which of the 8 ultrasound metrics do serial changes best predict positive response to NAC.

The predictive ability of serial change in each ultrasound metric from baseline to end of chemotherapy type will be analyzed statistically. We will systematically combine all possible groupings of serial changes in any two ultrasound outcome metrics. We will then statistically analyze the combined ability to predict positive response to NAC.

2.2.6 Determine if combinations of changes over time in any ultrasound outcome metrics correlate with positive response to NAC.

We will systematically combine all possible groupings of changes over time in any two ultrasound outcome metrics. We will then statistically analyze the combined ability to predict positive response to NAC.

2.2.7 Determine if combinations of serial change for any 2 ultrasound metrics predict positive response to NAC.

We will assess the predictive ability of serial change in ultrasound metrics from baseline to end of chemotherapy type treatment using ROC analysis.

2.2.8 Determine the combined performance of ultrasound metrics and mammography for predicting a positive response to NAC.

For ultrasound outcome metrics with an AUC exceeding 0.75 from 2.2.1, 2.2.3, 2.2.5, and 2.2.7, their combined diagnostic accuracy with mammography measures (mass size, density, shape, and margins) will be analyzed statistically.

2.2.9 Determine the sensitivity, specificity and PPV of ultrasound outcome metrics to predict positive response to NAC.

Best-balanced cutpoints from the highest performing ultrasound metrics in 2.2.1 and 2.2.4 will be derived used to analyze sensitivity, specificity, and PPV of reduction in tumor size.

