6.0 STATISTICAL CONSIDERATIONS

6.1 Study Design/Study Endpoints

For Aims #1 and #2, the ability of ultrasound biomarkers to discriminate binary outcomes (malignant/benign and responsive/unresponsive to treatment) will be analyzed using logistic regression. The area under the receiver operating characteristic curve (AUC) will be quantified, with separate models fit for each of the eight ultrasound biomarkers. Because most ultrasound biomarkers are continuous measures, the best-balanced cutpoints optimizing sensitivity and specificity will be calculated, using Youden's Index. Outcome discrimination by dual biomarkers will be analyzed in 28 separate models with combinations of any two ultrasound biomarkers. The combined benefit of ultrasound and mammography will be analyzed in 32 models, by adding a single mammography metric (lesion size, density, shape, or margins) to each of the eight ultrasound biomarker models. In Aim #2, the relationship between biomarker values and tumor size, biomarker values and change in tumor size, and change in biomarker values and change in tumor size will be analyzed by linear regression. These correlations will be analyzed in separate models for each of the eight ultrasound biomarkers, in models of dual ultrasound biomarkers, and in models combining mammography metrics with ultrasound biomarkers.

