6.2 Sample Size and Accrual

A total of 80 participants will be recruited for this study. The study will be conducted in 40 women with diagnosed BIRADS-4 or -5 masses and in 40 women with malignant masses undergoing neoadjuvant chemotherapy.

We project 12 of the 40 women in our study will have malignant cancer, and 12 of 40 will have masses that do not respond to NAC. Given this, we expect 80% power to detect a minimum AUC of 0.70 (95% CI: 0.51 – 0.89). This is consistent with the diagnostic accuracy previously reported for malignancy detection by ultrasound biomarkers, which have ranged from AUC values of 0.67 to 0.99.^{5,10}

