6.3.1.2 What is the combined diagnostic accuracy of any 2 ultrasound metrics?

The incremental value of using a second ultrasound metric will be analyzed by constructing separate ROC curves for combinations of any 2 ultrasound metrics.

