6.3.1.3 What is the combined diagnostic accuracy of ultrasound metrics and mammography?

We will select ultrasound metrics with an AUC exceeding 0.75 in C.1.a-b, and their combined diagnostic accuracy with mammography measures (mass size, density, shape, and margins) will be analyzed in separate ROC curves.

6.3.1.4 Which cutpoints for ultrasound metrics detect malignancy with optimum sensitivity and specificity?

Best-balanced cutpoints from the highest performing ultrasound metrics in 6.3.1.1 will be derived from ROC curves, using Youden's Index. These cutpoints will be used to analyze the PPV.

6.3.2 Aim #2: Correlate ultrasound-derived stiffness, elasticity, viscosity, and anisotropy with response to treatment.

In 40 women with newly diagnosed invasive breast cancer who are scheduled to begin clinically indicated NAC, ARFI, VisR, and DDAI imaging will be performed (as described in Aim #1) at baseline, early within each chemotherapy type, and at the conclusion of each chemotherapy type over the course of treatment.

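### Objective 2.1.3 asks whether mammography improves ROC performance, but the only analysis compares in-sample ROC curves of nested models, which favours a yes even for an uninformative descriptor

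*Combined protocol and SAP*

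**What the plan says.** Objective 2.1.3 applies "For ultrasound outcome metrics (singly or combined) with AUC exceeding 0.75 in 2.1.1 and 2.1.2". For these metrics it will determine whether adding mammographic size, density, shape and margins "improves ROC performance relative to not combining with mammography". That is a with-versus-without question with a yes or no answer.

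The method is in two places. Section 6.1 specifies logistic regression and builds 32 models "by adding a single mammography metric (lesion size, density, shape, or margins) to each of the eight ultrasound biomarker models". Section 6.3.1.3 says that, for the selected metrics, "their combined diagnostic accuracy with mammography measures (mass size, density, shape, and margins) will be analyzed in separate ROC curves".

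Section 6.3.1.2 treats a second ultrasound metric in the same style: "The incremental value of using a second ultrasound metric will be analyzed by constructing separate ROC curves".

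Section 6.2 sets the size at 40 women per aim and states: "We project 12 of the 40 women in our study will have malignant cancer, and 12 of 40 will have masses that do not respond". The second count refers to the neoadjuvant chemotherapy group.

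For these comparisons Section 6 gives no test of the added term, test of the AUC difference, minimum worthwhile gain, internal validation or multiplicity rule.

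**The concern.** The model with the mammographic descriptor contains the ultrasound-only model. Both are fitted by maximum likelihood to the same women and then scored in them. The larger model can use chance patterns in the added term, so its apparent AUC tends to be higher even when the term carries no information. With 12 events the tendency is not small.

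Drawing the two curves therefore does not separate real added value from overfitting. Someone who follows the plan as written has only two apparent curves to compare, and that comparison is biased towards concluding that mammography helps. At stake is the credibility of a positive answer to 2.1.3 and, to a lesser degree, of the incremental-value statement in 6.3.1.2.

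**Working it through.** **Inputs from the documents.** 40 women, 12 with and 28 without the event (6.2); entry gate of apparent AUC above 0.75 (2.1.3, 6.3.1.3); one descriptor added at a time, 8 × 4 = 32 models (6.1).

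**Assumed, because not stated.** How the descriptors are coded. The range examined is a single continuous or binary term, or 3, 4 or 5 unordered categories. Test level 0.05.

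**Step 1: the plan's own figure.** The documents give no figure for the mammography comparison. The nearest is the interval for an AUC of 0.70. The Hanley–McNeil variance, with a = A/(2−A) and b = 2A²/(1+A), is

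[A(1−A) + 11(a−A²) + 27(b−A²)] / (12 × 28).

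At A = 0.70, a = 0.5385 and b = 0.5765. The variance is (0.210 + 0.533 + 2.335)/336 = 0.00916, so SE = 0.0957. Then 0.70 ± 1.96 × 0.0957 gives 0.51 to 0.89, as printed. This confirms that 12 versus 28 is the plan's working basis. The stated power is a separate matter, and nothing here depends on it.

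**Step 2: apparent AUC when the added descriptor is noise.** Simulated trials used 12 versus 28 women and one normally distributed ultrasound metric, kept only if its apparent AUC exceeded 0.75. Descriptors were independent of outcome. Logistic models were fitted with and without them (1,500–2,000 trials per setting). The table shows the share of trials in which the apparent AUC rose.

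| True AUC of ultrasound metric | One single-term descriptor | 3 categories | 4 categories | 5 categories | At least one of four single-term descriptors |
|---|---|---|---|---|---|
| 0.75 | 65% | 83% | 91% | 96% | 98% |
| 0.80 | 64–66% | 80% | 88% | 95% | 96–97% |
| 0.85 | 63–64% | 81% | 91% | 96% | 95–97% |
| 0.90 | 62–63% | 80% | 89% | 95% | 95% |

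The single-term column averages over four interchangeable noise descriptors. For one single term the AUC falls in about 19–25% of trials and is otherwise unchanged.

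Mean gains are about 0.01 for a single term, 0.024–0.035 for 4 categories and 0.032–0.048 for 5. The best of four single-term descriptors gains 0.02–0.03 on average. If all four single-term descriptors were entered together, the AUC would rise in 93–94% of trials, by 0.03–0.05 on average.

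**Step 3: the second ultrasound metric (6.3.1.2).** This comparison has no gate. With a first metric of true AUC 0.75, one added continuous noise term raises the apparent AUC in 68–71% of trials, by 0.018 on average.

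**Step 4: the same noise under other criteria.**
- Likelihood-ratio test of one single-term descriptor at 0.05: rejects in about 6–7% of trials. With 3–4 degrees of freedom it rejects in about 8–10%.
- The same test on four descriptors, unadjusted: at least one rejection in about 22–27%. As a check, 1 − (1 − 0.065)⁴ = 0.24.
- Leave-one-out AUC: higher with the noise term in about 21% (400 trials).
- DeLong test on the fitted scores: under 1%, so it is very conservative for nested models.

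**The case against.** The plan never says that any numerical rise counts as improvement. The criterion is undefined, and under a formal test the false-positive rate would be low. This stands, and it is why every rate in Step 2 is conditional on reading a higher curve as improvement. It does not remove the point: a yes or no question is posed and the only analysis named is the pair of curves.

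A reader might infer that a single noise descriptor would pass in over 90% of trials. The documents do not support that. They give no coding, lesion size could well be continuous, and a single term raises the AUC in about two thirds of trials. Rates near or above 90% need about 4–5 unordered categories, the best of four descriptors, or all four entered together. Simulations that ignore the 0.75 gate also overstate the gains: at true AUC 0.75 they give 0.051 and 0.066 for 4 and 5 categories, against 0.035 and 0.048 with the gate.

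A reader might also extend the charge to 2.2.8 and 6.3.2.8. Those sections ask for the combined performance of ultrasound and mammography and state no with-versus-without comparison. They cannot be said to answer yes by construction. What remains there is that the reported AUC will be optimistic. Likewise, 6.3.1.2 speaks of incremental value but states no decision rule.

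Finally, the study is described as exploratory, its endpoints are the ultrasound metrics, and clinical management is unaffected. That limits the consequence. It does not make an in-sample comparison of nested models informative.

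**Conclusion.** The point holds for objective 2.1.3 with its methods in 6.1 and 6.3.1.3, and in weaker form for 6.3.1.2. The added-value question is to be answered from apparent ROC curves of nested models in 40 women, which biases the answer towards improvement. If a higher curve is taken as improvement, pure noise gives a yes in about 62–67% of trials for one single-term descriptor and in about 96% for at least one of four. For one descriptor in 4–5 unordered categories it is about 90–95%.

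These figures assume the projected 12 versus 28 split, a normally distributed ultrasound metric that passes the gate, and descriptors unrelated to outcome. The category counts are assumptions. For 2.2.8 and 6.3.2.8 the conclusion is only that the combined AUC is optimistic. The change is advisable and inexpensive; the exploratory study can proceed as designed.

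**What to change.** - **Criterion.** In 6.3.1.3, and in 6.3.1.2 for incremental value, judge improvement by a likelihood-ratio test of the added term in the nested logistic models. Use a penalised fit, such as Firth's, where a category contains women of one outcome only. The error rates above are for the ordinary test; the penalised version was not simulated.
- **Multiplicity.** Adjust for the number of tests, or label the step exploratory and draw no yes or no conclusion. A Bonferroni level would be 0.05/4 = 0.0125 for four descriptors on one metric, or 0.05/32 = 0.0016 over all 32 models.
- **Effect size.** Report the bootstrap or cross-validated optimism-corrected AUC difference in place of the gap between two apparent curves. The correction should repeat the 0.75 selection step.
- **Aim 2.** In 6.3.2.8 report optimism-corrected AUCs.
- **Optional.** Prespecify descriptor coding with few degrees of freedom, accepting some loss of detail.

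The cost is SAP wording, a little more analysis work and less favourable AUC figures. No additional patients, visits or data are needed.
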